6.3 SUMMARIES OF CONDUCT OF STUDY

Enrollment, protocol violations, and discontinuations from the study will be listed. The incidence of treatment discontinuation for reasons other than disease progression will be tabulated.

Data related to the administration of study treatment components as well as any dose modifications will be listed. The number of doses, treatment cycles, average dose received, for each treatment component will be summarized using descriptive statistics (mean, standard deviation, median, and range).

6.4 SUMMARIES OF DEMOGRAPHIC AND BASELINE CHARACTERISTICS

Demographic and baseline characteristics, such as age, sex, race, and duration of malignancy, will be summarized using descriptive statistics (mean, standard deviation, median, and range) for continuous variables and frequencies and percentages for categorical variables.

6.5 SAFETY ANALYSES

The safety analysis will be performed on the primary population; additional safety analysis will be performed on the ITT population.

The safety analyses will be performed separately for each study phase (i.e., dose escalation and expansion).

Safety will be assessed through summaries of adverse events, changes from baseline in laboratory test results, laboratory data with values outside of the normal ranges, ECGs, and vital signs.

All adverse events occurring on or after the first study treatment will be summarized by mapped term, appropriate thesaurus levels, and NCI CTCAE v4.0 grade. All serious adverse events, adverse events of special interest, and selected events will be summarized and listed.

Deaths reported during the treatment period and during post-treatment follow-up will be listed.

Relevant laboratory and vital sign data will be displayed by time, with Grade 3 and 4 values identified as appropriate.

6.6 EFFICACY ANALYSES

6.6.1 Primary Efficacy Endpoint

The efficacy analysis will be performed on the primary population. Additional efficacy analysis will be performed on the ITT population.

Patients who received lenalidomide at the RP2D during the dose-escalation phase will be pooled with patients treated in the expansion phase.

The primary efficacy analysis will be estimation of the proportion of patients achieving a CR at EOI, as determined by the IRC through use of the PET-CT–based Lugano 2014 criteria (see [Appendix 3](#)). Point estimates will be presented, along with the corresponding two-sided 90% Clopper-Pearson exact CIs. Patients without an EOI tumor assessment will be considered non-responders.

6.6.2 Secondary Efficacy Endpoints

The secondary efficacy analyses will be estimation of the proportion of patients achieving each of the following endpoints:

- CR at EOI, as determined by the investigator on the basis of PET-CT scans
- CR at EOI, as determined by the IRC and by the investigator on the basis of CT scans alone
- Objective response (defined as a CR or PR) at EOI, as determined by the IRC and by the investigator on the basis of PET-CT scans
- Objective response (defined as a CR or PR) at EOI, as determined by the IRC and by the investigator on the basis of CT scans alone
- Best response of CR or PR during the study, as determined by the investigator on the basis of CT scans alone.

For all secondary efficacy endpoints, point estimates will be presented, along with the corresponding two-sided 90% Clopper-Pearson exact CIs. Patients without a post-baseline tumor assessment will be considered non-CRs and non-responders, respectively.

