During induction treatment, all patients will have a CT scan performed at the end of Cycle 2 to confirm absence of early disease progression. Because of the potential for tumor flares with immunotherapies, which result in early apparent radiographic progression (pseudoprogression/tumor immune infiltration), including the appearance of new lesions followed by delayed response (Wolchok et al. 2009), patients whose CT scans meet criteria for disease progression may continue to receive study treatment at the discretion of the investigator and following discussion with the Medical Monitor if a moderate increase is seen in one lesion only or if at least two of the following criteria are met:

- Absence of symptoms and signs, including worsening of laboratory values (e.g., increased LDH) that indicate unequivocal disease progression
- No decline in Eastern Cooperative Oncology Group (ECOG) Performance Status
- Absence of tumor progression at critical anatomical sites (e.g., leptomeningeal disease) that cannot be managed by protocol-allowed medical interventions

Patients with radiographic evidence of progression at the end of Cycle 2 who continue to receive study treatment per the above criteria should have a CT scan repeated 4–8 weeks later.

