6.2 DEFINITION OF ANALYSIS POPULATIONS

The following populations are defined:

- The primary population will include patients who received at least one dose of each component of the combination.
- The intent-to-treat (ITT) population will include all patients enrolled in the study.

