6.6.3 Exploratory Efficacy Endpoints

For patients who have positive PET scans at EOI: CR at 12 months, as determined by the IRC and by the investigator on the basis of PET-CT scans.

Point estimates will be presented, along with the corresponding two-sided 90% Clopper-Pearson exact CIs. Patients without a post-baseline tumor assessment will be considered non-CRs and non-responders, respectively.

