Appendix 1 Schedule of Assessments (cont.)

- ^{gg} Includes CT scan of the neck (if clinically indicated), chest, abdomen, and pelvis. If contrast is medically contraindicated (e.g., patients with contrast allergy or impaired renal clearance), MRI scans of the chest, abdomen, and pelvis (and neck, if clinically indicated) and a non-contrast CT scan of the chest may be performed. Combined PET/CT scanners may be used to collect diagnostic CT scans, but only according to the technical guidelines in the imaging manual. The screening CT scan must be performed within 35 days prior to Day 1 of Cycle 1.
- ^{hh} Perform at the end of Cycle 2 (within 7 days prior to Day 1 of Cycle 3) and at 12, 18, and 24 months after initiation of induction treatment, within 14 days prior to treatment administration. Patients with radiographic evidence of progression at the end of Cycle 2 who continue to receive study treatment per criteria defined in Section 3.1.1 should have a CT scan repeated 4–8 weeks later.
 - ⁱⁱ Perform only if not done within the previous 3 months.
 - ^{jj} Perform every 6 months.
- ^{kk} Bone marrow biopsy and aspirate must be performed within approximately 3 months prior to Day 1 of Cycle 1.
- ^{ll} For patients with bone marrow involvement at screening, a repeat assessment will be performed at EOI if there is radiologic evidence of a complete response, and during maintenance or at EOM if there is radiologic evidence of a complete response or if clinically indicated (e.g., if there is clinical suspicion of progressive disease in the bone marrow with no radiologic evidence of progression).
- ^{mm} Refer to Sections 4.3.2.4 and 4.3.2.5 for details on dosing and schedule. At each cycle, each patient will be supplied with only enough lenalidomide for that cycle. During maintenance treatment, lenalidomide will be administered for a maximum of 12 months.
- ⁿⁿ Patient may be assessed every 2 months if atezolizumab has been discontinued and maintenance treatment is continued with obinutuzumab single agent

Appendix 2
Pharmacokinetic and Immunogenicity Sampling Schedule for Obinutuzumab, Atezolizumab, and Lenalidomide

Study Visit		Serum Obinutuzumab PK Sample ^{a,b,c}	Serum Atezolizumab PK Sample ^a	Serum Obinutuzumab HAHA Sample ^a	Serum Atezolizumab Anti-Therapeutic Antibody Sample ^a	Plasma Lenalidomide PK Sample ^{a,d}
Induction during Dose Escalation and Expansion (Cycles 1–6; 28-day cycles)						

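### Does the missing-scan rule in Sections 6.6.2 and 6.6.3 let unscanned patients fall out of the secondary and 12-month response rates?

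*Combined protocol and SAP*

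**What the plan says.** Section 6.6.1 sets the primary analysis: IRC-assessed PET-CT complete response (CR) at EOI, in the primary population, with a supplementary ITT analysis. Its missing-data rule is "Patients without an EOI tumor assessment will be considered non-responders". It also says "Patients who received lenalidomide at the RP2D during the dose-escalation phase will be pooled with patients treated in the expansion phase".

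Section 6.6.2 describes the secondary analyses as "estimation of the proportion of patients achieving each of the following endpoints". It lists five items: investigator PET-CT CR at EOI, CT-only CR at EOI, PET-CT objective response at EOI, CT-only objective response at EOI, and best CT response over the whole study. Its missing-data rule is "Patients without a post-baseline tumor assessment will be considered non-CRs and non-responders, respectively".

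Section 6.6.3 repeats that sentence for an exploratory endpoint: "For patients who have positive PET scans at EOI: CR at 12 months, as determined by the IRC and by the investigator".

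Section 6.2 gives the denominators. "The primary population will include patients who received at least one dose of each component of the combination". The ITT population is everyone enrolled. Neither requires a scan.

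On imaging, Section 3.1.1 states that "all patients will have a CT scan performed at the end of Cycle 2 to confirm absence of early disease progression". Appendix 1 schedules PET-CT at screening, at EOI, and at 12 months for patients whose EOI PET-CT is positive (footnote ff). EOI scans are due only after at least two induction cycles (footnote ee).

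**The concern.** The two rules name different patients for endpoints read at the same visit. Someone who has the Cycle 2 CT and then misses the EOI scan is a stated failure for the primary endpoint. That person does have a post-baseline assessment, so the Section 6.6.2 sentence does not name them. They could then count as a failure for IRC PET-CT CR and be absent from investigator PET-CT CR, which would blur the comparison of the two.

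In Section 6.6.3 the sentence has no effect at all. Everyone in the 12-month group has an EOI PET, which is itself post-baseline. Footnote ff times the 12-month PET relative to a treatment administration, so patients who never start maintenance or stop it early may have no scan due. Those are the patients for whom a rule would matter.

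The study is open-label and single-arm. Leaving out unscanned patients can only raise a response rate or leave it unchanged, so any freedom to do so would work in the regimen's favour.

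**Working it through.** **1. Reproduce the plan's interval.** Two-sided 90% Clopper-Pearson limits for x responders of n are BetaInv(0.05; x, n−x+1) and BetaInv(0.95; x+1, n−x). For the 0.60 row of Table 14, x = 24 and n = 40:

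- lower = BetaInv(0.05; 24, 17) = 0.4578
- upper = BetaInv(0.95; 25, 16) = 0.7306

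These round to the tabulated (0.46, 0.73).

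**2. Who falls outside the Section 6.6.2 sentence.** Patients who stop before two cycles are not due an EOI scan and will mostly have no post-baseline scan, so the sentence covers them. Patients who stop induction for an adverse event have their own EOI window (Appendix 1, footnote c). What remains is patients with an earlier scan and a missed EOI scan.

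| Section 6.6.2 endpoint | Does the sentence fit? |
|---|---|
| Best CT response over the study | Yes, exactly |
| CT-only CR and CT-only objective response at EOI | No, if the Cycle 2 CT was done |
| PET-CT CR and PET-CT objective response at EOI | Only if tumor assessment is read as the modality the endpoint uses |

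On the last row, the Cycle 2 scan is CT only, so the first scheduled post-baseline PET-CT is the EOI one. Read by modality, having no post-baseline PET-CT and having no EOI PET-CT pick out the same scheduled patients, and the PET-CT endpoints have no gap. The plan does not state this reading, so the conclusion does not rest on it.

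**3. What happens to a patient the sentence does not name.** The denominator comes from Section 6.2, by dosing or enrolment. The numerator is patients achieving the endpoint. A patient with no EOI scan has not been shown to achieve CR or response at EOI, so contributes 0 to the numerator and 1 to the denominator. Leaving that patient out would need an evaluable-for-response set, and the plan defines none. With 24 responders among 40 dosed patients the result is 24/40 = 60.0% however many of the other 16 lack an EOI scan.

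The same logic applies at 12 months. The group is fixed by the EOI PET result, not by having a 12-month scan, so a member without that scan has no documented CR.

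**4. Size if patients were dropped anyway.** The rate becomes x/(n−m), where m is the number dropped. The documents give no rate of missing scans, so m is assumed. As loose context, 75 of 86 patients completed induction in the cited obinutuzumab-lenalidomide study (Section 1.4.3.2). That leaves 11/86 = 12.8%, or about 5 of 40, though non-completers may still be scanned.

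| Case | Kept in | Dropped |
|---|---|---|
| EOI CR, m = 1 | 24/40 = 60.0% (45.8–73.1) | 24/39 = 61.5% (47.1–74.6) |
| EOI CR, m = 3 | 24/40 = 60.0% (45.8–73.1) | 24/37 = 64.9% (50.0–77.8) |
| EOI CR, m = 5 | 24/40 = 60.0% (45.8–73.1) | 24/35 = 68.6% (53.4–81.3) |
| Pooled n = 46, m = 3 | 28/46 = 60.9% (47.7–73.0) | 28/43 = 65.1% (51.5–77.1) |
| 12-month CR, m = 3 | 4/16 = 25.0% (9.0–48.4) | 4/13 = 30.8% (11.3–57.3) |

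The 28 responders of 46, the 16 EOI-PET-positive patients and the 4 later CRs are also assumed. Sixteen is the count of non-CRs at the 60% planning rate (40 − 24). It is an upper bound at that rate, because non-CRs also include patients with no EOI scan and PET-negative patients who fail the bone-marrow requirement in Appendix 3.

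**The case for a change.** The best case for a change is that the authors saw a need for a missing-scan rule in all three sections and wrote a different one in two of them. A rule that names one group invites the inference that others are handled differently. In Section 6.6.3 the wording also refers to non-responders although the only endpoint there is CR, which suggests text carried across without adaptation. Agreeing the rule before the data are seen would cost two sentences.

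The textual part of this stands: the sections are not aligned, and the Section 6.6.3 sentence is empty. The inference about exclusion is weaker. Section 6.6.2 states neither an analysis population nor the pooling of escalation patients. Both appear only in Section 6.6.1 and must carry forward for Section 6.6.2 to work at all. The EOI non-responder rule sits in the same place, and in the synopsis it falls under the general efficacy heading. The Section 6.6.2 sentence can be read as adding what best response needs, since that endpoint has no single visit.

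The 12-month endpoint is the softer spot, because no rule there does any work and some early stoppers will have no scan due. But it is an exploratory, descriptive estimate in a small subgroup, and an analysis sentence would not produce the missing scans.

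**Conclusion.** No change follows. This is a drafting mismatch that analysts following the plan would resolve the same way: every patient in the defined population stays in the denominator, and a patient without the required scan is counted as not achieving the endpoint. On that reading no rate changes. The primary endpoint has its own explicit rule and is unaffected either way.

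The conclusion rests on taking Section 6.2 and the proportion-of-patients wording at face value, and on no response-evaluable set being introduced later. If patients were dropped despite this, the illustrated rise at n = 40 is 1.5 points for one patient (61.5 − 60.0), 4.9 for three (64.9 − 60.0) and 8.6 for five (68.6 − 60.0). The 90% interval is 27.3 points wide (73.1 − 45.8). The endpoints concerned are secondary or exploratory and are estimated without a test. Aligning the wording would record what the analysis already does, without altering a result.

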6.6.3 Exploratory Efficacy Endpoints

For patients who have positive PET scans at EOI: CR at 12 months, as determined by the IRC and by the investigator on the basis of PET-CT scans.

Point estimates will be presented, along with the corresponding two-sided 90% Clopper-Pearson exact CIs. Patients without a post-baseline tumor assessment will be considered non-CRs and non-responders, respectively.

6.7 PHARMACOKINETIC ANALYSES

Plasma/serum concentrations of obinutuzumab, atezolizumab, and lenalidomide will be tabulated, summarized, and plotted after appropriate grouping. As appropriate, PK parameters (e.g., AUC, time to maximum concentration, maximum concentration, and half-life) may also be calculated, tabulated, and summarized after appropriate grouping. Additional PK and PK/PD analyses (e.g., population modelling, including pooled analyses across studies) may also be performed as appropriate. If done, these additional analyses may be reported separately from the Clinical Study Report. At the discretion of the Sponsor, all analyses may be extended to include relevant-biotransformation products of lenalidomide.

6.8 IMMUNOGENICITY ANALYSES

The numbers and proportions of post-treatment HAHA- or anti-therapeutic antibody-positive patients and HAHA- or anti-therapeutic antibody-negative patients at baseline and during both the treatment and follow-up periods will be summarized. The relationship between HAHA or anti-therapeutic antibody status and safety, efficacy, and PK endpoints will be explored as appropriate.

6.9 BIOMARKER ANALYSES

Exploratory analyses of biomarkers related to tumor biology and study treatment mechanisms of action will be conducted. Analyses will assess the prognostic and/or predictive value of candidate biomarkers with respect to both IRC- and investigator-assessed outcomes. Specifically, the association between candidate biomarkers and PET-CT–defined CR rate and OR rate, and potentially other measures of efficacy and safety, will be explored to assess potential prognostic or predictive value. These analyses may not be included in the final study report because of their exploratory nature. In addition to analysis in the context of this study, data will also be explored in aggregate with data from other studies.

6.10 INTERIM ANALYSES

It is anticipated that at least one interim analysis will be conducted during the expansion phase of the study, when at least 15 patients treated at the RP2D of lenalidomide have been evaluated for PET-CT–defined CR at the EOI. Additional analyses will be conducted every 4 months to guide early stopping of enrollment for safety on the basis of observed toxicities. Stopping rules for excess toxicity, including fatal adverse events, have been included (see Section [6.11](#)).

During the expansion phase, a modified version of the predictive probability design (Lee and Lui 2008) may be used to guide early stopping for futility by comparing the observed proportion of patients who achieve a PET-CT–defined CR at EOI with that in historical controls. The earliest interim analysis would occur after at least 15 patients have been evaluated for PET-CT–defined CR at EOI.

If, at any time, an interim analysis suggests that the proportion of patients achieving a PET-CT–defined CR is lower or higher than expected, the IMC will review the data and decide whether to recommend an early decision to stop enrollment. Interim analysis decision rules will be based on the modified version of the predictive probability that the trial will have a positive outcome if carried out to completion and will use the historical control data available at the time of analysis.

Additional review of safety and/or efficacy data by the IMC may be requested by and carried out at the discretion of the Medical Monitor. Further details regarding the rules and guidelines of data review will be provided in an IMC charter.

6.11 STOPPING RULES FOR SAFETY

In the event that any of the following criteria are met at any time in the course of the study, the IMC will be immediately convened to review and provide a recommendation for further conduct of the study:

- Fatal adverse events $\geq 10\%$
- Grade 3–4 adverse events $\geq 75\%$

The fatal adverse event threshold of 10% is derived from the completed GADOLIN study (Sehn et al. 2015) and the ongoing external study GALEN (Morschhauser et al. 2017), in which the occurrence rates of Grade 5 adverse events were 6% and 3.4%, respectively. Based on these two studies, the assumed historical control fatal adverse event rate is 5%, and with a 5% addition as a trigger for IMC review, a threshold rate of 10% is used for the stopping rules. The fatal adverse events will be continuously monitored during the conduct of the study and if the number of fatal adverse events reach the pre-specified threshold, the IMC will be immediately convened to decide whether to continue or stop the study (see [Table 15](#)). For each of these incidence rates, the minimized false positive probabilities and the true positive probability of correctly triggering an IMC safety review when the observed fatal adverse event rates are 5% higher than the historical control rate are presented.

Table 15 Early Stopping Rules Based on Number of Fatal Adverse Events

Interim look, n	# (rate, %) of fatal (Grade 5) AE(s) required for an IMC review	Probability of early stopping ^a	
		Probability of correct stop if true experimental regimen fatal AE rate =10% (historical control rate + 5%)	Probability of incorrect stop if true experimental regimen fatal AE rate =5%
27–30	2 (7%)	59%	19%
31–40	2 (5%)	78%	32%
41–45	3 (7%)	67%	19%

AE=adverse event; IMC=Internal Monitoring Committee.

Note: The assumed historical control fatal adverse event rate is 5%.

^a Assessed for upper limit of the interim look sample size (i.e., for n=30, 40, 45).

In addition to fatal adverse events, Grade 3/4 adverse events, which represent severe non-fatal events, will be closely monitored. The threshold of 75% for Grade 3/4 adverse events is derived from the external study GALEN (Morschhauser et al. 2017) and the completed study GADOLIN (Sehn et al. 2015), where the occurrence rates of Grade 3/4 adverse events were 57% and 62%, respectively.

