3.1.4 Internal Monitoring Committee

An IMC will monitor patient safety throughout the study. The IMC will include the Sponsor representatives from Clinical Science, Drug Safety, Biostatistics, and Statistical Programming and Analysis. In addition to the ongoing assessment of the incidence and nature of adverse events (particularly, Grade ≥ 3 events), serious adverse events, deaths, and laboratory abnormalities performed by the investigator and the Medical Monitor, the IMC will review data supporting the determination of the RP2D and cumulative data at regular intervals, every 4 months for safety and efficacy, and ad-hoc if safety concerns arise between the planned regular 4-month intervals, during the expansion phase.

Predefined stopping rules for excess toxicity, including fatal adverse events, have been included in Section 6.11. In the event that any of the stopping rules criteria are met at any time during the course of the study, enrollment of patients will be paused while an IMC meeting is immediately convened to review and provide a recommendation on further conduct of the study (e.g., consider study discontinuation).

At the time of each review, the IMC will make appropriate recommendations (e.g., the study should continue as planned, additional analyses should be performed, enrollment should be held pending further safety evaluations).

Decisions will be made in consideration of the totality of the available data. Ad hoc meetings may be called in addition to scheduled meetings, as necessary, to provide recommendations on management of any potential new safety signals. At the time when all patients have completed or discontinued the maintenance treatment, regular IMC assessments will no longer take place. Ad hoc meetings may be called at the discretion of the Medical Monitor in case of newly identified safety signals. Specific operational details such as the committee's composition, frequency and timing of meetings, members' roles and responsibilities, and data to be reviewed will be detailed in an IMC charter.

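### The Grade 3–4 safety trigger in Section 6.11 has no first look or denominator and, read literally, would usually pause enrolment falsely; for fatal events the 10% criterion conflicts with Table 15, whose counts and probabilities also disagree

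*Combined protocol and SAP*

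**What the plan says.** Section 6.11 opens with "In the event that any of the following criteria are met at any time in the course of the study" and lists two percentages: fatal adverse events of at least 10% and Grade 3–4 adverse events of at least 75%. Section 6.11 itself only convenes the Internal Monitoring Committee (IMC). Section 3.1.4 adds that "enrollment of patients will be paused while an IMC meeting is immediately convened", and Section 3.1.3 says the same for the expansion phase.

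The Grade 3–4 threshold is justified by two external studies, "where the occurrence rates of Grade 3/4 adverse events were 57% and 62%, respectively". Nothing more is given for this rule.

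The fatal rule has more detail. Its 10% threshold is an assumed historical rate of 5% plus 5 points. Section 6.11 also says "The fatal adverse events will be continuously monitored during the conduct of the study" and points to Table 15, which gives death counts and single-look probabilities of a correct stop (true rate 10%) and an incorrect stop (true rate 5%):

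| Patients | Deaths | Correct | Incorrect |
|---|---|---|---|
| 27–30 | 2 (7%) | 59% | 19% |
| 31–40 | 2 (5%) | 78% | 32% |
| 41–45 | 3 (7%) | 67% | 19% |

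A footnote says the probabilities are evaluated at n = 30, 40 and 45.

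**The concern.** A bare percentage applied from the first patient is very unstable. One Grade 3–4 event in patient 1 is a rate of 100%, in a population where the plan itself expects such an event in about six patients in ten. If the IMC follows the text, a pause would usually reflect small numbers rather than excess toxicity. Repeated false alarms would delay a 46-patient trial and blunt the response to a real signal.

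For fatal events the problem is different. There are two rules: one acts at 10% at any time, the other at 5% to 7% from 27 patients on. If the probabilities printed for the second are not those of its printed counts, the IMC cannot know how often either rule will trigger falsely.

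**Working it through.** **Inputs.** Grade 3–4 threshold 75%, with background rates 57% and 62% (Section 6.11). Fatal threshold 10%, assumed background 5%, source studies 3.4% and 6% (Section 6.11). Planned total about 46 (Section 3.1.1). The 80% used below as a rate worth detecting is my assumption; the plan names none.

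**1. Reproduce Table 15.** The single-look probability of at least r deaths among n patients is P(X ≥ r), with X binomial (n, p). For the first row at 5%: P(X ≥ 2 | n = 30) = 1 − 0.95^30 − 30 × 0.05 × 0.95^29 = 1 − 0.215 − 0.339 = 0.446, against a printed 19%. All rows, as correct / incorrect:

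| n | Table 15 prints | Printed count | One death more |
|---|---|---|---|
| 30 | 59% / 19% | ≥2: 81.6% / 44.6% | ≥3: 58.9% / 18.8% |
| 40 | 78% / 32% | ≥2: 92.0% / 60.1% | ≥3: 77.7% / 32.3% |
| 45 | 67% / 19% | ≥3: 84.1% / 39.2% | ≥4: 67.1% / 18.7% |

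No cell matches the printed counts. All six match one death more, so the printed probabilities are those of exceeding the printed count, not reaching it.

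**2. Cumulative probability.** Because the rules act at any time, the relevant quantity is the chance of crossing at any look. Let a_n(x) be the probability of x events among n patients with no earlier crossing. Then a_n(x) = a_(n−1)(x)(1 − p) + a_(n−1)(x − 1)p. At each look, the mass at or above the threshold is moved to the trigger total. This assumes a look after every patient, each fully observed before the next.

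**3. Grade 3–4 rule.** The trigger at n is a count of at least 0.75n. At n = 1 one event suffices, with probability p: 57% or 62%. The next possible crossing is 3 of 4, needing a non-event followed by three events: (1 − p)p³ = 0.43 × 0.185 = 8.0%, or 0.38 × 0.238 = 9.1%. So 65.0% or 71.1% is reached by patient 4. Continuing to n = 46:

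| First look | True 57% | True 62% |
|---|---|---|
| n = 1 | 68.5% | 76.3% |
| n = 6 | 33.4% | 47.3% |
| n = 10 | 22.1% | 36.3% |
| n = 20 | 9.8% | 21.8% |
| n = 27 | 4.9% | 13.9% |

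At a true 80%, a first look at n = 27 triggers with probability 91%, against 98.5% from patient 1.

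**4. Fatal rule.** Under the 10% criterion, one death among the first 10 patients triggers: 1 − 0.95^10 = 40.1% at a true 5%. The cumulative figure is 46.0% by n = 26 and 48.5% by n = 46 (33.7% at 3.4%, 57.0% at 6%). Under Table 15 applied continuously over n = 27–45 at 5%, the printed 2, 2 and 3 deaths give 60.7%; 3, 3 and 4 deaths give 33.0%.

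**5. Sensitivity to the denominator.** Suppose events arise over time and every treated patient counts at once. Assume uniform accrual over 17 months (the 4-year study less about 30 months of treatment and screening), exponential onset times, and triggers counted during accrual only. The literal Grade 3–4 rule then triggers falsely with these probabilities, at true 57% and 62%:

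| Mean onset | True 57% | True 62% |
|---|---|---|
| 0.5 months | 47% | 59% |
| 1 month | 31% | 41% |
| 2 months | 15% | 19% |
| 3 months | 9% | 10% |

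The documents give no onset times.

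**The case against.** A trigger brings a pause and an immediate review of the totality of the data, not termination. For a new three-drug combination, a sensitive early alarm may be deliberate. Operating details are left to an IMC charter, which is not among the documents. Most of the Grade 3–4 figure comes from patient 1, and a sensible committee would not pause on that. All this is fair and limits the harm. But Section 3.1.4 makes the pause automatic once a criterion is met, and a charter should not have to supply the first look for a rule the protocol applies at any time. The denominator point also stands: Section 6.5 analyses safety separately by phase, and Section 6.11 does not say who counts.

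Three stronger readings are tempting and are not supported.

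- A reader might infer that each trigger is more likely than not to fire falsely. The 10% fatal criterion alone reaches 48.5% at the assumed 5%, just under half.
- A reader might infer that the fatal rule has no minimum number of patients. Section 6.11 ties fatal events to Table 15, which starts at 27; the defect is a conflict between two rules.
- A reader might infer that letting Table 15 govern would cure the fatal rule. With its printed counts the cumulative false-trigger probability at 5% is 61%, higher than the 48.5% of the percentage criterion.

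**Conclusion.** The Grade 3–4 rule misfires as written: 68% to 76% cumulative false triggering at the plan's own background rates, if each patient is fully observed before the next look. The result depends on the missing first look (22% to 36% from n = 10, 5% to 14% from n = 27) and on the undefined denominator. With slow onset and all treated patients counted, it can fall to about 10%. That a false pause is more likely than not therefore holds only for the literal, fully observed reading.

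For fatal events, two findings need no such assumption: the 10% criterion and Table 15 are different rules, and Table 15's probabilities do not belong to its counts. The true single-look false-trigger probabilities of the printed counts are 45%, 60% and 39%, not 19%, 32% and 19%. The 61% cumulative figure does assume complete data and a look after every patient.

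**What to change.** In Section 6.11:

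- **Grade 3–4 rule.** Define the denominator (which phase or phases, and how much follow-up before a patient counts) and a first look. For example, start at n = 27 as Table 15 does and act at the smallest count reaching 75%: 21 of 27, 23 of 30, 30 of 40, 35 of 46. This leaves the threshold unchanged. Print cumulative trigger probabilities at 57%, 62% and 80%.
- **Fatal rule.** Reconcile the 10% criterion with Table 15 so that one rule applies. Correct the mismatch between Table 15's counts and probabilities before the table governs anything; whether the counts or the probabilities were intended is for the sponsor to say. Print cumulative rather than single-look probabilities.

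The cost is protocol wording and two small tables. The downside is that the formal Grade 3–4 trigger starts later, with detection at a true 80% falling from 98.5% to 91%. Until then, early patients are covered by the dose-limiting toxicity rules in the escalation phase and by the four-monthly and ad hoc IMC reviews in the expansion phase.
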